8.2.2 Baseline descriptive statistics

8.2.2.1 Demographic/anthropometric variables

The variables age, weight, height, BMI and waist circumference will be described by the mean, median, standard deviation, minimum, maximum, interquartile range and 95% confidence interval.

The study will examine whether there are statistically significant differences in these variables according to the severity of COPD and type of patient (exposed/unexposed), using the Student's t-test and one-way ANOVA test in the case of compliance with the assumptions necessary for the use of parametric tests, or the Mann-Whitney U test and the Kruskal-Wallis H test if otherwise, as appropriate.

The frequency distribution of patients will be given according to sex:

- Male
- Female

The likelihood ratio test will be used to study whether there are statistically significant differences in the sex of patients depending on the severity of COPD, while Pearson's Chi-square test or Fisher's exact test will be used to examine statistically significant differences between sex and the type of patient (exposed vs. unexposed).

8.2.2.2 Alcohol consumption

The absolute and relative frequency of patients who consume alcohol will be presented, considering as such those with an intake of ≥ 80 g/day for at least the previous year. Using Pearson's Chi-squared test or Fisher's exact test for 2x2 tables or likelihood ratio for mXn tables, we will study whether statistically significant differences are observed in alcohol consumption and the two patient subpopulations established according to the severity of COPD and type of patient (exposed/unexposed).

8.2.2.3 Relevant medical history

The absolute and relative frequency of patients with at least one relevant condition in their history will be given, as well as each of the personal histories described:

- High blood pressure
- Dyslipidemia
- Type II diabetes mellitus
- Metabolic syndrome
- Heart failure
- Chronic kidney disease
- Cirrhosis
- History of neoplasia (solid organ and hematologic)
- Previous pneumonia in the last year
- Other relevant history

The study will examine whether there are statistically significant differences in the presence of a relevant history depending on the severity of COPD and type of patient (exposed/unexposed) using the likelihood ratio test and Pearson's Chi-Square test or Fisher's exact test, as appropriate.

8.2.3 Effectiveness analysis

8.2.3.1 Study of exacerbations

A detailed analysis of the total number of exacerbations reported by the study patients will initially be performed. The absolute and relative frequency of patients who have reported at least two moderate exacerbations or one severe exacerbation per year (exacerbator patient) will be given.

The following indices will be calculated:

- NEPA (number of exacerbations patient/year) = Total no. of exacerbations reported by patients/ Patient follow-up time^{*)}
- NEPA Mild = Total no. of mild exacerbations/Patient follow-up time
- NEPA Moderate = Total no. of moderate exacerbations/Patient follow-up time
- NEPA Severe = Total no. of severe exacerbations/Patient follow-up time
- NEPA Moderate/severe = Total no. of moderate_severe exacerbations/Patient follow-up time

The following will also be calculated in the subpopulation of exposed patients:

- NEPA_pre_PCV13 = Total no. of exacerbations reported by the patient prior to receiving the PCV13 / Time to vaccination with PCV13^{**)}
- NEPA_pre_PCV13 (moderate/severe) = Total no. of moderate/severe exacerbations reported by the patient prior to receiving the PCV13 / Time to vaccination with PCV13^{**)*)}
- NEPA_post_PCV13 = Total no. of exacerbations reported by the patient after receiving the PCV13 / Time since vaccination with PCV13^{***)}
- NEPA_post_PCV13 (moderate/severe) = Total no. of moderate/severe exacerbations reported by the patient prior to receiving the PCV13 / Time since vaccination with PCV13^{***)}

*) Time from the date of COPD diagnosis to the date of the last follow-up visit. If the date of diagnosis of the disease is unknown, it will be computed as two years before the date of inclusion of the patient in the study

**) Time from date of COPD diagnosis to date of PCV13 vaccination

***) Time from vaccination with PCV13 to date of the last follow-up

Each of the indices calculated above will be described using the main measures of central tendency and dispersion (mean, median, standard deviation, confidence intervals, minimum, maximum and interquartile range).

The Student's t test, one-way ANOVA or its non-parametric equivalents, the Mann-Mann U test or Kruskal-Wallis H test will be used to determine if statistically significant differences are observed in NEPA, NEPA Mild, NEPA Moderate, NEPA Severe and NEPA Moderate/Severe according to the severity of COPD and type of patient (exposed/unexposed). In order to determine the impact of PCV13 vaccination on exacerbations, paired data comparisons will be made between (NEPA_pre_PCV13 vs. NEPA_post_PCV13) and (NEPA_pre_PCV13 (moderate/severe) vs. NEPA_post_PCV13 (moderate/severe)), using the Student's t-test for paired data or its non-parametric equivalent, the Wilcoxon test.

In order to study which subgroups of patients obtain a greater benefit from vaccination

with PCV13 according to COPD severity, paired data comparisons will be made between (NEPA_pre_PCV13 vs. NEPA_post_PCV13) and (NEPA_pre_PCV13 (moderate/severe) vs. NEPA_post_PCV13 (moderate/severe)), in each of the four patient subpopulations established based on disease severity.

In order to determine the factors associated with the presence of an exacerbator patient, a logistic regression model will be constructed, whose dependent variable is (exacerbator/non-exacerbator patient) and, as independent variables, all those possible factors that have been significant in the univariate models ($p_{value} < 0.25$), following the methodology of Hosmer-Lemeshow.

- ❖ Vaccine exposure (PCV13 yes/no)
- ❖ COPD severity (Grade I, Grade II, Grade III, Grade IV)
- ❖ Age
- ❖ Sex
- ❖ Time since diagnosis of the disease
- ❖ Patient with stable treatment for at least three months
- ❖

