## 6. RATIONALE AND BACKGROUND

Patients with chronic obstructive pulmonary disease (COPD) have been demonstrated to have an increased risk of pneumococcal disease. Pneumonia is frequent among patients hospitalized for COPD exacerbations and is associated with increased health care utilization and higher mortality. Nonpneumonic COPD exacerbations predict increased risk of subsequent exacerbations. Among community acquired pneumonia (CAP) patients with the highest severity of disease who require hospitalization, COPD is the most common comorbidity. These two diagnoses, CAP and acute exacerbations of COPD (AECOPD), come together when COPD patients acquire AECOPD caused by CAP.

Exacerbations are a significant component of the clinical course in COPD. Furthermore, as COPD progresses, exacerbations become more frequent. COPD exacerbations are defined as a complex of two or more respiratory symptoms (worsening dyspnea, cough, sputum production, chest tightness, or wheezing) related to the underlying COPD, with duration of 3 days or more, that require a change in treatment. Acute exacerbations of COPD (AECOPD) have a great impact on health status, disease progression, and prognosis. Up to 50%–70% of AECOPD can be attributed to respiratory infections by viruses or bacteria, even more in the most severe patients. They are often associated with the colonization of airways by multiple bacteria or viruses of low virulence that in normal conditions are parts of the normal flora of the upper airway.

Some studies have identified factors independently associated with bacterial growth, such as current smoking and *H. influenzae*; longer periods between exacerbations and *S. pneumoniae*; or decrease in FEV1 and *P. aeruginosa*. Traditionally, bacterial identification has been defined depending on the severity of the COPD, since *S. pneumoniae* and *M. catharralis*, are isolated in patients with predicted FEV1 >50%, and *H. influenzae*, Enterobacteriaceae and *P. aeruginosa* in those with FEV1 <50%.

Therefore, considering *S. pneumoniae* appears to be more frequent in patients with mild/moderate COPD, these subjects might be the most benefited from a preventive approach targeting this pathogen.

Redacted

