### **8.2.1. Inclusion criteria**

Patients must meet all of the following inclusion criteria to be eligible for inclusion in the study:

1. Patient  $\geq 18$  years diagnosed with COPD (any stage, the subgroups for the analysis would be based on COPD severity grade)

Redacted

2. Evidence of a personally signed and dated informed consent document indicating that the patient (or a legally acceptable representative) has been informed of all pertinent aspects of the study.
3. Ability to understand and complete the required QoL questionnaires
4. At least 2 years of clinical history available that includes records of previous moderate/severe exacerbations, influenza and pneumococcal vaccination history comorbidities and previous treatments.
5. Spirometry data\* (maximum 6 months old, or if not available at enrollment, to be performed as per normal clinical practice at visit 1 +/- one month)

\*Subjects with FEV1 <40 should be less than 20% of the total study population (related to the microbiological etiology dependent on severity)

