4 HYPOTHESIS AND ROLE OF DISCUSSION

The statistical significance value is set at $p < 0.05$. The SPSS statistical package version 19.0 or later will be used.

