5 ANALYSIS SYSTEMS / POPULATIONS

Considering that 37% of COPD patients will have one moderate/severe exacerbation per year, and assuming that at least 35% of patients will follow their doctor's vaccination

recommendation,³ to have at least 200 vaccinated COPD patients with moderate/severe exacerbations, a total of 1541 eligible subjects should be included in the analysis.

With 35% of patients vaccinated with PCV13, enrolling 1541 eligible subjects with COPD would provide approximately 540 patients in the PCV13 cohort and 1000 patients in the unexposed cohort.

Assuming that 37% of unexposed patients will present one moderate/severe exacerbation per year,² with 70% of the patients remaining in the study after 1 year, this sample size would provide 91% power to detect a statistically significant reduction of 10% in moderate/severe COPD exacerbations with PCV13 after 1 year. Assuming an additional 30% dropout in the second year, the study sample size would provide 91% power to detect a statistically significant reduction of 14% in moderate/severe COPD exacerbations with PCV13 after 2 years.

Time	PCV13		Unexposed		Power	Retention rate
	Sample size	% exacerbation	Sample size	% exacerbation		
Enrollment	540		1000			
1 year	378	27%	700	37%	91.43%	70% from enrollment
2 years	264	60%	490	74%	91%	70% from year 1

5.1 **FULL ANALYSIS**

The statistical analysis of this study will be carried out with all those evaluable patients with COPD, recruited by the Spanish sites participating in the study and who meet the following selection criteria:

5.1.1 **Inclusion Criteria**

Patients must meet all of the following inclusion criteria to be eligible for inclusion in the study:

1. *Aged 18 years or older at the time consent is given*
2. *Patient diagnosed with COPD (any stage, subgroups for analysis will be based on COPD severity)*
3. *Evidence of a personally signed and dated informed consent document indicating that the patient has been informed of all pertinent aspects of the study.*
4. *Ability to understand and complete the required quality of life questionnaires*
5. *Patients with at least 2 years of previous clinical history available relating to (if applicable) history of moderate/severe exacerbations, influenza and pneumococcal vaccination history, comorbidities and previous treatments*
6. *Spirometry data* (maximum 6 months old, or if not available at enrollment, to be performed as per normal clinical practice at visit 1 ± one month)*

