- For comparison of independent samples, the Pearson's Chi-squared test or the Fisher's exact test for 2x2 tables or likelihood ratio for mXn tables will be used for qualitative variables. The Student's t-test, one-way ANOVA or its non-parametric equivalents, the Mann-Mann U test or Kruskal-Wallis H test, will be used for quantitative variables.
- For comparison of paired samples, the McNemar's test will be used for qualitative variables and the Student's t-test or Wilcoxon's test for quantitative variables.
- The study will seek to identify factors associated with the occurrence of exacerbations throughout the follow-up period; to that end, a multivariate logistic regression analysis will be performed, where the dependent variable will be the occurrence of exacerbations (Yes/No) during the study. Vaccination with PCV13 and significant variables in the univariate model will be used as possible risk factors: demographic characteristics, influenza vaccination, smoking habit, etc. In addition, potential confounding variables will be considered: exacerbator phenotype, comorbidities, COPD severity, FEV1 (no control possible based on the study design).
- Appropriate tests will be performed accordingly to determine if the necessary requirements are fulfilled for the use of parametric tests.
- Estimates will be performed with a 95% confidence interval. The SPSS statistical package, version 19.0 or later, will be used.

8.2 **STATISTICAL ANALYSIS**

8.2.1 **Patient disposition**

The absolute and relative frequency of evaluable patients will be determined. In the subpopulation of non-evaluable patients, the frequency distribution will be presented based on the reasons for non-evaluation:

- Patient under 18 years of age at the time of obtaining informed consent
- Not diagnosed with COPD of any grade (patients diagnosed with COPD less than 2 years after inclusion in the study should not be included)
- At least two years of prior medical records are not available relating to (if applicable):
 - History of moderate/severe exacerbations
 - History of influenza vaccination (date)
 - History of pneumococcal vaccination (date)
 - Comorbidities
 - Previous treatments
- No spirometry data available
- Inability to understand and complete the required quality of life questionnaires
- No evidence of a personally signed and dated informed consent document indicating that the subject has been informed of all pertinent aspects of the study

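### The exacerbator outcome in the PCV13 logistic model has no time window and its named covariates omit earlier exacerbations, so the PCV13 odds ratio is biased in a direction set by who gets vaccinated

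*SAP*

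**What the plan says.** SAP 8.2.3.1 starts from all exacerbations reported by the study patients and then classifies "patients who have reported at least two moderate exacerbations or one severe exacerbation per year (exacerbator patient"). No calendar window is attached, nothing ties the status to inclusion or vaccination, and no rule says which year counts. Later in the section, "a logistic regression model will be constructed, whose dependent variable is (exacerbator/non-exacerbator patient"). The named predictors are PCV13 exposure, COPD severity, age, sex, time since diagnosis and stable treatment, followed by an empty bullet. Entry is by univariate p below 0.25.

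The general exacerbation rates in the same section divide by time from COPD diagnosis to last visit. SAP section 6 lists exacerbation frequency in earlier years as well as during follow-up among the primary endpoints.

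SAP 8.1 describes another logistic model, whose outcome is any exacerbation, yes or no, within the study period. There, "potential confounding variables will be considered: exacerbator phenotype, comorbidities, COPD severity, FEV1 (no control possible based on the study design").

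Protocol section 6 states: "Nonpneumonic COPD exacerbations predict increased risk of subsequent exacerbations". Protocol 8.2.1, criterion 4, requires: "At least 2 years of clinical history available that includes records of previous moderate/severe exacerbations". Protocol 8.2 allows vaccination before or after inclusion. The definitions under Protocol Table 1 count a patient as vaccinated only from 15 days after the dose; the SAP does not carry that rule over.

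**The concern.** An outcome that may be dated before the exposure cannot measure an effect of that exposure. If the status is drawn from the whole record, and one qualifying year is enough, a patient whose only severe exacerbation came before PCV13 enters the model as a vaccinated exacerbator.

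Even with a dated outcome, exacerbation history would remain a strong candidate confounder. By the protocol's own account it predicts later exacerbations, and it may also influence who is vaccinated. The two SAP sections treat the same characteristic differently: it is an outcome in 8.2.3.1, and in 8.1 a confounder said to be beyond control, although the records needed to adjust for it are an entry requirement.

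This is the only multivariable model containing PCV13 that the effectiveness section specifies, so its odds ratio is likely to be read as the adjusted vaccine effect.

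**Working it through.** **1. The plan's own figure.** The documents give no figure for this model. The nearest is the one-year power, which supplies the event rate and effect size used below.

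- Inputs, from SAP section 5: "Assuming that 37% of unexposed patients will present one moderate/severe exacerbation per year"; 27% with PCV13; 378 against 700 patients; stated power 91.43%. SAP section 4: "The statistical significance value is set at" p below 0.05, with no sidedness given, so two-sided is used.
- Pooled proportion = (378 × 0.27 + 700 × 0.37) / 1078 = 0.335.
- Null SE = √[0.335 × 0.665 × (1/378 + 1/700)] = 0.0301.
- Alternative SE = √[0.27 × 0.73/378 + 0.37 × 0.63/700] = 0.0292.
- Power = Φ[(0.10 − 1.96 × 0.0301) / 0.0292] = 91.9%, or 90.9% with continuity correction. The stated figure reproduces.
- Implied rate ratio = ln(1 − 0.27) / ln(1 − 0.37) = ln 0.73 / ln 0.63 = 0.68.

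**2. First simulation, no vaccine effect.** 400,000 patients per scenario. Assumptions not in the documents: 0.45 moderate and 0.15 severe events per year with gamma heterogeneity of shape 1 (about 37% with an event per year), two years of history plus two of follow-up, and uptake depending on any prior event.

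| Uptake, prior event v none | Undated, 4 years | Follow-up only | Follow-up, adjusted for prior count |
|---|---|---|---|
| 45% v 30% | 1.42 | 1.23 | 0.99 |
| 40% v 33% | 1.19 | 1.10 | 1.00 |

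Equal uptake gives about 1.00. With shape 0.7 the first row becomes 1.50, 1.30 and 1.00. If per year is read as an average over the whole window instead of any single year, the undated 1.42 becomes 1.36.

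**3. Second simulation, selection varied in both directions.** 35% vaccinated; half of them at inclusion and half at month 12; 25% of events severe; any qualifying year counts. Selection is the odds ratio of being vaccinated given a prior event. For comparison, 45% v 30% is (0.45/0.55)/(0.30/0.70) = 1.91.

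| Selection OR | 0.5 | 1 | 1.5 | 2 | 3 |
|---|---|---|---|---|---|
| No effect, undated | 0.68 | 0.99 | 1.27 | 1.50 | 1.82 |
| No effect, follow-up only | 0.79 | 0.99 | 1.14 | 1.26 | 1.40 |
| No effect, follow-up, adjusted | 1.00 | 0.99 | 1.00 | 0.99 | 0.98 |
| Rate ratio 0.68, undated | 0.58 | 0.86 | 1.09 | 1.28 | 1.57 |
| Rate ratio 0.68, year 2 only, adjusted | 0.61 | 0.59 | 0.59 | 0.60 | 0.60 |

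Year 2 is used in the last row because by then every vaccinated patient has been vaccinated.

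**4. False conclusions at the planned size.** 300 simulated studies of 1540 patients per scenario, with 0.70 × 0.70 = 49% retained:

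- No effect, undated outcome: significant harm in 34%, 76% and 97% of runs at selection OR 1.5, 2 and 3; significant benefit in 72% at 0.5.
- Rate ratio 0.68, no selection: significant benefit in 13.7% of runs with the undated outcome, against 65.3% with the year-2 adjusted model.

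**The case against.** **The SAP does contain a window and does name the confounder.** SAP 8.1 limits its outcome to the study period and lists exacerbator phenotype. This stands to the extent that a reader who infers that the whole SAP lacks any time limit or any thought of adjustment goes too far. It does not cure 8.2.3.1. The 8.1 text belongs to a different outcome, only promises to consider the confounder, and does not separate pre- from post-vaccination time in patients vaccinated after inclusion.

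**The diagnosis-date footnote belongs to the rates, not to the exacerbator definition.** True. Counting the whole record is one reading of an undated definition, though it fits the surrounding text. A single old severe event also qualifies only if one year suffices; averaged over four years it is 0.25 per year. The bias survives that reading (1.36).

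**Other factors may enter.** The list ends in an empty bullet and any factor with univariate p below 0.25 may be included, so prior exacerbations could be added. Nothing guarantees it. The simulations leave out severity and time since diagnosis, so their odds ratios are not those of the planned model.

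**A reader might infer that PCV13 will look harmful.** The documents do not support that. The protocol cites a recommendation to vaccinate all patients with mild, moderate or severe COPD, and the reasons for non-vaccination in Protocol 8.1 do not mention exacerbations. The uptake gradients are assumptions.

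**A reader might infer that the cohort comparison cannot address primary objective 1.** That is also too strong. SAP 8.2.3.1 assigns vaccine impact to paired pre/post rates and compares rates between exposed and unexposed patients. This point does not test those analyses.

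**Conclusion.** The defect is real and confined to the logistic model of SAP 8.2.3.1, with a related gap in adjustment in 8.1. The outcome may include pre-vaccination events, and nothing ensures adjustment for exacerbation history that the protocol requires to be available.

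The direction of the bias depends on who is vaccinated: toward harm if patients with more prior exacerbations are vaccinated more often, toward benefit if less often. With equal uptake there is no false effect, but a true one is diluted, from an odds ratio of 0.59 to 0.86 at the plan's implied rate ratio of 0.68. Under no effect and 45% v 30% uptake, the undated odds ratio is about 1.42.

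These sizes rest on the assumed event mix, heterogeneity, vaccination timing and uptake. The pattern of directions, and the return to about 1.00 after dating and adjustment when there is no effect, held in both simulations.

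**What to change.** 1. In SAP 8.2.3.1, define the model outcome from prospective follow-up only, state how per year is judged, and give exposed and unexposed patients a comparable time zero and window length. For patients vaccinated after inclusion, treat PCV13 as time-varying using the protocol's 15-day rule, or use matched index dates or person-time rates. Do not start the window 15 days after PCV13 for exposed patients alone. That shortens only their window: with no vaccine effect and half of the vaccinated receiving PCV13 at month 12, it gives a spurious adjusted odds ratio of about 0.61 to 0.70, depending on how qualifying years are counted.
2. Force the moderate/severe count from the two years before inclusion into this model and the SAP 8.1 model, whatever its univariate p. For patients vaccinated before inclusion, use the available pre-vaccination history as a rate and state that it may be shorter than two years: someone vaccinated one year before inclusion is guaranteed only one year of it by criterion 4.
3. Delete the closing parenthesis in SAP 8.1 that says control is not possible, and reconcile the two model descriptions.

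The cost is SAP wording and one covariate that criterion 4 already requires. Historic events no longer add to the outcome count, and handling time-varying exposure or index dates makes the analysis slightly more complex.

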## **Study procedures**

Subjects identified with COPD will be informed about the study and invited to participate by investigators at the time of their routine control visits. All therapies will be prescribed according to the updated National COPD Guidelines (GesEPOC) indicating among other therapies active reduction of risk factors, influenza and pneumococcal vaccination (with PCV13) in all patients with mild, moderate or severe COPD. All the patients will be counselled to stop smoking and advised on life-style modifications. Any vaccination will be prescribed according to clinical practice and not related to the decision to include the subjects in the study. Subjects may be vaccinated before or after inclusion in the study.

Study will include periodic scheduled visits for all patients, to complete a total follow up of 2 years (see Table 1).

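### The SAP's exacerbator label is a per-year count with no stated window or part-year rule, so with unequal follow-up the logistic outcome depends on how long a patient is followed

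*SAP*

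**What the plan says.** SAP 8.2.3.1 will report the frequency of patients with "at least two moderate exacerbations or one severe exacerbation per year (exacerbator patient) will be given". It does not say whether the count is an annualised rate, must be met in any single year, or refers to one particular year. It gives no period, no rule for part-years and no minimum follow-up.

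The same section then builds a logistic model "whose dependent variable is (exacerbator/non-exacerbator patient". PCV13 exposure heads the candidate factors. The listed candidate nearest to a time term is "Time since diagnosis of the disease", which is disease duration rather than time on study, and factors enter only if the univariate p-value is below 0.25.

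The only patient follow-up time the section defines belongs to the NEPA rates: "Time from the date of COPD diagnosis to the date of the last follow-up visit". There is a fallback: "If the date of diagnosis of the disease is unknown, it will be computed as two years before the date of inclusion". The SAP does not say that this clock applies to the exacerbator label.

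The protocol plans 24 months for all (Study procedures: "Study will include periodic scheduled visits for all patients, to complete a total follow up of 2 years"). SAP section 5 expects 70% to remain at year 1 and goes on: "Assuming an additional 30% dropout in the second year". SAP section 7 replaces no missing values outside the SGRQ.

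**The concern.** Exacerbations are small whole numbers. A threshold of 2 moderate or 1 severe per year is therefore not the same hurdle at 6, 12, 18 and 24 months, and the unstated rule decides which patients find it easier to meet. The logistic model treats the label as if everyone had been observed equally. If vaccinated and unvaccinated patients are followed for different lengths of time, part of that difference appears as a PCV13 odds ratio even when the vaccine does nothing. Such a difference is plausible: the cohorts are not randomised, and the protocol allows vaccination before or after inclusion, so becoming exposed can itself depend on time in the study.

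**Working it through.** **1. The plan's own retention (SAP section 5; Protocol 8.5).** PCV13: 540 × 0.7 = 378, then 378 × 0.7 = 264.6 (stated 264). Control: 1000 × 0.7 = 700, then 700 × 0.7 = 490. Completers: (264 + 490)/1540 = 49%. The figures reproduce, and retention is the same in both cohorts.

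**2. Events needed for the label.** Let T be years of follow-up.
- *Annualised over study time:* moderate ≥ 2T or severe ≥ T, rounded up. Month 6: 1 moderate or 1 severe. Month 12: 2 or 1. Month 18: 3 or 2. Month 24: 4 or 2.
- *Any one study year:* 2 moderate or 1 severe within a year, for everyone. Longer follow-up gives more chances.
- *Annualised on the diagnosis-to-last-visit clock, two years of history:* month 6 is 2 × 2.5 = 5 moderate (or 3 severe); month 24 is 2 × 4 = 8 moderate (or 4 severe). With ten years of history the moderate bars are 21 v 24.

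**3. Chance of the label, same risk for everyone.** The 37% yearly risk is the plan's. Read as the chance of at least one event at a constant Poisson rate, it gives −ln(0.63) = 0.462 events per year. The severe share is not in the documents. I assume 20%, so 0.370 moderate and 0.092 severe per year. P = 1 − P(too few moderate) × P(too few severe).

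| Reading | 6 mo | 12 mo | 18 mo | 24 mo |
|---|---|---|---|---|
| Annualised, study time | 20.6% | 13.7% | 2.7% | 2.2% |
| Any one study year | 6.0% | 13.7% | 18.9% | 25.5% |

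Examples: annualised at 6 months, any single event qualifies, so 1 − exp(−0.231) = 20.6%. Any one year at 24 months: 1 − (1 − 0.137)² = 25.5%. For severe shares of 0 to 30%, annualised is 20.6% v 1.4–3.6% (6 v 24 months) and any one year is 2.3–7.8% v 15.2–30.5%. With overdispersion (gamma-Poisson, k = 1) the annualised row becomes 22.7%, 18.3%, 8.6%, 8.2%. On the diagnosis clock with two years of history the chance is 0.4% v 0.1%.

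**4. Effect on the PCV13 odds ratio with no vaccine effect.** Cohort chance = (1 − r)·P(a) + r(1 − r)·P(b) + r²·P(24), where r is yearly retention and a and b are the months at which year-1 and year-2 leavers are last seen. If r = 0.70 in both cohorts, as planned, the odds ratio is 1.0. Now assume a 10-point gap that averages 70% overall: 76.5% exposed, 66.5% unexposed.

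| Leaving months (a/b) | Annualised | Any one year |
|---|---|---|
| 6 / 18 | 6.6% v 8.5%, OR 0.76 | 19.7% v 17.5%, OR 1.16 |
| 6.5 / 18.5 | 3.0% v 3.4%, OR 0.88 | 20.0% v 17.8%, OR 1.15 |
| 1 / 12 | 4.6% v 5.3%, OR 0.87 | 17.6% v 14.6%, OR 1.25 |

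First cell: 0.235 × 0.206 + 0.180 × 0.027 + 0.585 × 0.022 = 6.6%; 0.335 × 0.206 + 0.223 × 0.027 + 0.442 × 0.022 = 8.5%. Overdispersed, that odds ratio is 0.87.

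**5. Who carries the label (annualised, r = 0.70).** Year-1 leavers are 0.30 × 0.206/0.078 = 79% of exacerbators if last seen at month 6 (54% overdispersed), but 0.30 × 0.038/0.051 = 22% if last seen at month 1 and year-2 leavers at month 12.

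**The case against.** Four objections carry weight.
- **The contrast of one moderate event for a month-6 leaver with four for a completer.** A reader might take this as what the SAP prescribes. It follows only from annualising over study time, which the SAP never states; on its one defined clock the bars are 5 v 8, and on the any-one-year reading they are equal. This objection stands, and the contrast has to stay conditional.
- **Retention.** The size table assumes equal retention, under which the odds ratio is unbiased. This stands; the 10-point gap is my assumption. But an assumption in a size calculation does not secure equal follow-up in a non-randomised cohort.
- **Sensitivity to leaving dates.** Month 6.0 is exactly where one event meets two per year. At 6.5 months the annualised chance falls from 20.6% to 6.5%. So a claim that most exacerbators are early leavers, or that the vaccine would look harmful, is not supported in general.
- **Role of the model.** SAP 8.2.3.1 assesses vaccine impact through the NEPA comparisons; the exacerbator model explores associated factors. The candidate list also ends in an empty bullet, so a follow-up term cannot be fully excluded. Both are true and limit the weight of the point. None is stated, however, and the model still yields a PCV13 odds ratio if the factor enters.

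**Conclusion.** The point holds as a defect in the outcome definition. Under each of the three readings checked, the label depends on length of follow-up, and the plan expects about half the patients to leave before 2 years. What the documents do not settle is the size or direction of any bias in the PCV13 coefficient: none with equal retention; about 0.76 to 0.88 annualised, or 1.15 to 1.25 on the any-one-year reading, with the assumed 10-point gap and no vaccine effect. These figures rest on the plan's 37% risk, a constant rate common to all patients, an assumed 20% severe share and assumed leaving dates. That an unstated rule decides the sign is reason enough to settle the rule before analysis. It should be changed, but it does not by itself undermine the NEPA analyses.

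**What to change.** In SAP 8.2.3.1, define exacerbator on one fixed window for everyone: at least 2 moderate or 1 severe exacerbation with onset within 12 months after inclusion (visit 0). Analyse time to meeting that definition, with cumulative incidence and a Cox model, and censor patients who leave earlier without meeting it. Inclusion is the start because unvaccinated patients have no vaccination date. Enter PCV13 as a time-updated exposure from 15 days after vaccination, which is the protocol's own rule for counting a patient as vaccinated (definitions under Table 1). Those definitions also fix the onset date of an exacerbation, and the NEPA formulas already use the vaccination date, so no new data item is needed.

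Costs: events after month 12 do not enter this outcome, although the primary objective is set at 2 years; they stay in the rate analyses. The logistic model for this outcome is replaced by a Cox model, which is a change of method and not only of wording. Censoring also assumes that, given the covariates, leaving is unrelated to exacerbation risk, and the SAP should say so.
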